11.1.4.3 Evaluation of Best Overall Response (RECIST)

The best overall response is the best response recorded from the start of the treatment until disease progression/recurrence (taking as reference for PD the smallest measurements recorded since the treatment started). The patient’s best response assignment will depend on the achievement of both measurement and confirmation criteria.

For Patients with Measurable Disease (i.e., Target Disease)

Target Lesions	Non-Target Lesions	New Lesions	Overall Response	Best Overall Response when Confirmation is Required*
CR	CR	No	CR	≥4 wks Confirmation**
CR	Non-CR/Non-PD	No	PR	≥4 wks Confirmation**
CR	Not evaluated	No	PR	
PR	Non-CR/Non-PD /not evaluated	No	PR	
SD	Non-CR/Non-PD /not evaluated	No	SD	Documented at least once ≥4 wks from baseline**
PD	Any	Yes or No	PD	no prior SD, PR, or CR
Any	PD***	Yes or No	PD	
Any	Any	Yes	PD	

* See RECIST 1.1 manuscript for further details on what is evidence of a new lesion. ** Only for nonrandomized trials with response as primary endpoint. *** In exceptional circumstances, unequivocal progression in non-target lesions may be accepted as disease progression.
 
Note: Patients with a global deterioration of health status requiring discontinuation of treatment without objective evidence of disease progression at that time should be reported as “symptomatic deterioration.” Every effort should be made to document the objective progression even after discontinuation of treatment.
				

For Patients with Nonmeasurable Disease (i.e., Non-Target Disease)

Non-Target Lesions	New Lesions	Overall Response
CR	No	CR
Non-CR/non-PD	No	Non-CR/non-PD*
Not all evaluated	No	not evaluated
Unequivocal PD	Yes or No	PD
Any	Yes	PD

* “Non-CR/non-PD” is preferred over ‘stable disease’ for non-target disease since SD is increasingly used as an endpoint for assessment of efficacy in some trials so to assign this category when no lesions can be measured is not advised
		

11.1.5 *Progression-Free Survival*

PFS is defined as the duration of time from start of treatment to time of progression or death, whichever occurs first.

11.1.6 *Duration of Response*

The duration of overall response is measured from the time measurement criteria are met for CR or PR (whichever is first recorded) until the first date that recurrent or progressive disease is objectively documented (taking as reference for PD the smallest measurements recorded since the treatment started).

11.1.7 *Overall Survival*

Status of patient survival will be reported to the CITN by the primary treating physicians on an every 6 months schedule.

11.1.8 *Response Review*

Imaging studies will be collected for a possible expert review of responses. Investigator determined responses will be chronicled and reported unless or until a central expert review takes place.

12. DATA REPORTING / REGULATORY REQUIREMENTS

AE lists, guidelines, and instructions for AE reporting can be found in Section 7.0 (Adverse Events: List and Reporting Requirements).

12.1 Data Reporting

Data collection for this study will be done exclusively through Medidata Rave. Access to the trial in Rave is granted through the iMedidata application to all persons with the appropriate Rave roles in the CTSU Regulatory Support System (RSS). To access iMedidata/Rave the site user must have an active CTEP IAM account ([check](https://ctepcore.nci.nih.gov/iam) at < <https://ctepcore.nci.nih.gov/iam> >). In addition, site users that are members of the CITN must have the appropriate Rave roles (Rave CRA, site PI, or Read-Only) in RSS at the enrolling site. To hold the Rave CRA role or CRA Lab Admin role, the user must hold a minimum of an AP registration type. To hold the Rave Site Investigator role, the individual must be registered as an NPIVR or IVR. Associates can hold read-only roles in Rave.

Upon initial site registration approval for the study in RSS, all persons with Rave roles assigned on the CITN roster will be sent a study invitation email from iMedidata. To accept the invitation, site users must log into the Select Login (<https://login.imedidata.com/selectlogin>) using their CTEP-IAM user name and password, and click on the “accept” link in the upper right corner of the iMedidata page. Please note, site users will not be able to access the study in Rave until all required Medidata and study specific trainings are completed. Trainings will be in the form of electronic learnings (eLearnings), and can be accessed by clicking on the link in the will be listed in the upper right pane of the iMedidata screen.

Users who have not previously activated their iMedidata/Rave accounts at the time of initial site registration approval for the study in RSS will also receive a separate invitation from iMedidata to activate their account. Account activation instructions are located on the CTSU website, Rave

tab under the Rave resource materials (Medidata Account Activation and Study Invitation Acceptance). Additional information on iMedidata/Rave is available on the CTSU website under the Rave tab at www.ctsu.org/RAVE/ or by contacting the CTSU Help Desk at [name] or by email at [contact].

12.1.1 Method

This study will be monitored by the Clinical Data Update System (CDUS) Version 3.0. Cumulative protocol- and patient-specific CDUS data will be submitted electronically to CTEP on a quarterly basis, either by FTP burst of data or via the CDS web application. Reports are due January 31, April 30, July 31, and October 31. Instructions for submitting data using the CDUS can be found on the CTEP Web site: (<http://ctep.cancer.gov/reporting/cdus.html>).

All AEs (both routine and expedited) that have occurred on the study and meet the mandatory CDUS reporting guidelines must be reported via the monitoring method identified above.

12.1.2 Responsibility for Data Submission

For CITN trials, it is the responsibility of the PI(s) at the site to ensure that all investigators at the CITN Sites understand the procedures for data submission for each CITN protocol and that protocol specified data are submitted accurately and in a timely manner to the CITN data management organization-via the electronic data capture system, Medidata Rave.

Data from Medidata Rave and CTEP-AERS is reviewed by the CITN data management organization on an ongoing basis as data is received. Queries will be issued by CITN data management organization directly within Rave. The queries will appear on the Task Summary Tab within Rave for the CRA at the CITN to resolve. Monthly web-based reports are posted for review by the Drug Monitors in the IDB, CTEP. Onsite audits will be conducted to ensure compliance with regulatory requirements, GCP, and NCI policies and procedures with the overarching goal of ensuring the integrity of data generated from NCI-sponsored clinical trials, which may be found on the CTEP (http://ctep.cancer.gov/protocolDevelopment/electronic_applications/adverse_events.htm) and CTSU websites.

The CITN data management organization will utilize a core set of eCRFs that are Cancer Data Standards Registry and Repository (caDSR) compliant (<http://cbiit.nci.nih.gov/ncip/biomedical-informatics-resources/interoperability-and-semantics/metadata-and-models>). Customized eCRFs will be included when appropriate to meet unique study requirements. The PI is encouraged to review the eCRFs, working closely with the CITN data management organization to ensure prospectively that all required items are appropriately captured in the eCRFs prior to study activation. The CITN data management organization will prepare the eCRFs with built-in edit checks to the extent possible to promote data integrity.

CDUS data submissions will be carried out by the CITN data management organization contractor, Axio. CDUS submissions are performed by Axio on a quarterly basis. The trial's lead institution is responsible for timely submission to the CITN data management organization via Rave, as above.

See Section 12.1.1 for details on CDUS reporting. As the data management center for this trial, Axio is responsible for compiling and submitting CDUS data to CTEP for all participants and for providing the data to the Principal Investigator for review.

12.2 CTEP Multicenter Guidelines

This protocol will adhere to the policies and requirements of the CTEP Multicenter Guidelines. The specific responsibilities of the PI and the Coordinating Center and the procedures for auditing are presented in Appendix B.

- The PI/Coordinating Center is responsible for distributing all IND Action Letters or Safety Reports received from CTEP to all participating institutions for submission to their individual IRBs for action as required. Submit documentation of reportable adverse events to [contact] and state in the subject line "Safety Report for *NCI protocol #*" or "Action Letter for *NCI protocol #*", as appropriate. A brief summary cover page on Coordinating Center letterhead is encouraged. These documents will be posted to the CTSU protocol web page and included in the next CTSU bi-monthly broadcast.
- Except in very unusual circumstances, each participating institution will order DCTD-supplied agents directly from CTEP. Agents may be ordered by a participating site only after the initial IRB approval for the site has been forwarded by the Clinical Research Site to the CTSU Regulatory Office for entry in the Regulatory Support System (RSS) and transmission to CTEP.

12.3 Collaborative Agreements Language

The agent(s) supplied by CTEP, DCTD, NCI used in this protocol is/are provided to the NCI under a Collaborative Agreement (CRADA, CTA, CSA) between the Pharmaceutical Company(ies) (hereinafter referred to as "Collaborator(s)") and the NCI Division of Cancer Treatment and Diagnosis. Therefore, the following obligations/guidelines, in addition to the provisions in the "Intellectual Property Option to Collaborator" (http://ctep.cancer.gov/industryCollaborations2/intellectual_property.htm) contained within the terms of award, apply to the use of the Agent(s) in this study:

1. Agent(s) may not be used for any purpose outside the scope of this protocol, nor can Agent(s) be transferred or licensed to any party not participating in the clinical study. Collaborator(s) data for Agent(s) are confidential and proprietary to Collaborator(s) and shall be maintained as such by the investigators. The protocol documents for studies utilizing Agents contain confidential information and should not be shared or distributed without the permission of the NCI. If a copy of this protocol is requested by a patient or patient's family member participating on the study, the individual should sign a confidentiality agreement. A suitable model agreement can be downloaded from: <http://ctep.cancer.gov>.
2. For a clinical protocol where there is an investigational Agent used in combination with

(an)other Agent(s), each the subject of different Collaborative Agreements, the access to and use of data by each Collaborator shall be as follows (data pertaining to such combination use shall hereinafter be referred to as "Multi-Party Data"):

- a. NCI will provide all Collaborators with prior written notice regarding the existence and nature of any agreements governing their collaboration with NCI, the design of the proposed combination protocol, and the existence of any obligations that would tend to restrict NCI's participation in the proposed combination protocol.
 - b. Each Collaborator shall agree to permit use of the Multi-Party Data from the clinical trial by any other Collaborator solely to the extent necessary to allow said other Collaborator to develop, obtain regulatory approval or commercialize its own Agent.
 - c. Any Collaborator having the right to use the Multi-Party Data from these trials must agree in writing prior to the commencement of the trials that it will use the Multi-Party Data solely for development, regulatory approval, and commercialization of its own Agent.
3. Clinical Trial Data and Results and Raw Data developed under a Collaborative Agreement will be made available to Collaborator(s), the NCI, and the FDA, as appropriate and unless additional disclosure is required by law or court order as described in the IP Option to Collaborator (http://ctep.cancer.gov/industryCollaborations2/intellectual_property.htm). Additionally, all Clinical Data and Results and Raw Data will be collected, used and disclosed consistent with all applicable federal statutes and regulations for the protection of human subjects, including, if applicable, the *Standards for Privacy of Individually Identifiable Health Information* set forth in 45 C.F.R. Part 164.
4. When a Collaborator wishes to initiate a data request, the request should first be sent to the NCI, who will then notify the appropriate investigators (Group Chair for Cooperative Group studies, or PI for other studies) of Collaborator's wish to contact them.
5. Any data provided to Collaborator(s) for Phase 3 studies must be in accordance with the guidelines and policies of the responsible Data Monitoring Committee (DMC), if there is a DMC for this clinical trial.
6. Any manuscripts reporting the results of this clinical trial must be provided to CTEP by the Group office for Cooperative Group studies or by the principal investigator for non-Cooperative Group studies for immediate delivery to Collaborator(s) for advisory review and comment prior to submission for publication. Collaborator(s) will have 30 days from the date of receipt for review. Collaborator shall have the right to request that publication be delayed for up to an additional 30 days in order to ensure that Collaborator's confidential and proprietary data, in addition to Collaborator(s)'s intellectual property rights, are protected. Copies of abstracts must be provided to CTEP for forwarding to Collaborator(s) for courtesy review as soon as possible and preferably at least three (3) days prior to submission, but in any case, prior to presentation at the meeting or publication in the proceedings. Press releases and other media presentations must also be forwarded to CTEP prior to release. Copies of any manuscript, abstract and/or press release/ media presentation should be sent to:

Email: [contact]

The Regulatory Affairs Branch will then distribute them to Collaborator(s). No publication,

manuscript or other form of public disclosure shall contain any of Collaborator's confidential/ proprietary information.

13. STATISTICAL CONSIDERATIONS

This section outlines the statistical analysis strategy and procedures for the study. If, after the study has begun, but before the conduct of any analysis, changes are made to primary and/or key secondary hypotheses or the statistical methods related to those hypotheses, then the protocol will be amended (consistent with ICH Guideline E-9). Changes to exploratory or other non-confirmatory analyses made after the protocol has been finalized, along with an explanation as to when and why they occurred, will be listed in the Clinical Study Report (CSR) for the study. Post hoc exploratory analyses will be clearly identified in the CSR. No separate Statistical Analysis Plan (SAP) will be issued for this study.

13.1 Responsibility for Analyses

The statistical analysis of the data obtained from this study will be the responsibility of the FHCRC as part of the CITN.

This trial is being conducted as an open-label study, i.e., patients, investigators, and trial personnel will be aware of patient treatment.

A single interim analysis will be conducted at the end of Stage 1 (Section 13.10). If at least 1 response is observed among the 9 enrolled patients, the trial will proceed to enroll an additional 15 patients in Stage 2.

13.2 Study Design/Endpoints

13.2.1 Primary Objective

- To determine the clinical efficacy of MK-3475 as the first systemic intervention for patients with advanced MCC

The primary endpoint will be ORR as measured by RECIST 1.1.

13.2.2 Secondary Objectives

- To determine the clinical activity of MK-3475 as the first systemic intervention for patients with advanced MCC

The secondary endpoints will be PFS, DOR, and OS, as measured by RECIST 1.1. The PFS will be determined at 16 months and compared to the historical PFS for patients treated with chemotherapy, which is 5% at 16 months.

13.2.3 Exploratory Objectives

- To determine the immune correlates of the clinical activity of MK-3475

The endpoints will include IHC and gene expression analysis focusing on delineating the immune components and immunologic milieu within the tumor before therapy. The IHC analyses performed will include, but is not limited to, MCPyV T-Ag, PD-1, CD8, and CD3. In addition, MCPyV viral DNA will be quantified in the tumor ([Section 2.5.2](#)).

Cellular and humoral MCPyV-specific immune responses will be assessed with ELISpot and serology assays in blood samples at baseline, after initiating MK-3475 therapy, and correlated with clinical responses over time. Among patients with corresponding MHC-peptide tetramers, pre- and post-treatment samples of circulating MCPyV-specific CD8 T cells will be isolated and subjected to deep immunophenotyping by mRNA expression analysis ([Section 2.5.3](#)).

13.3 Analysis Endpoints

13.3.1 *Efficacy Endpoints*

The primary and secondary efficacy endpoints are described below.

Objective response rate (ORR) is defined as the proportion of patients who have achieved CR or PR according to RECIST 1.1.

Progression-Free Survival (PFS) is defined as the time from randomization to PD or death, whichever occurs earlier, based upon investigator assessment using RECIST 1.1. Patients without documented PD/death will be censored at the last disease assessment date.

Duration of response (DOR) is defined as the time interval between the date of first response (CR/PR) and the date of progression.

Overall survival (OS) is defined as the time from randomization to death due to any cause. Patients without documented death at the time of analysis will be censored at the date last known to be alive.

13.3.2 *Safety Endpoints*

The primary safety endpoints are AEs graded using CTCAE (Version 5.0) criteria. Safety will be assessed by quantifying the toxicities and grades experienced by subjects who have received MK-3475 including AEs and SAEs. Safety will be monitored by cumulative data reviews throughout the trial.

Other safety endpoints include laboratory safety assessments, ECOG performance status, vital signs, and physical examinations.

Note: Patients discontinuing MK-3475 due to toxicity will still be considered evaluable for response.

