After a patient is discontinued from study therapy, an end of therapy visit should be performed as soon as possible following the decision to stop study drug treatment or in conjunction with last treatment visit if discontinuation of therapy is anticipated. A mandatory safety follow-up visit should be performed approximately 30 days after the last infusion of study medication. All AEs occurring within 30 days after the last dose of trial treatment will be recorded.

All patients who discontinue treatment due to progression will be followed for at least 30 days after their last dose of study drug or until initiation of a new anticancer treatment, whichever occurs first. After the safety follow-up visit, patients will be followed for survival via phone contact every 12 weeks.

Patients who discontinue study therapy without documented disease progression will have a mandatory safety follow-up visit approximately 30 days after the last infusion of study drug, and should continue to be monitored for disease status by radiologic imaging according to the guidelines described in the [Visit Requirements](#) and [Study Calendar](#) for post-treatment follow-up. Imaging may be performed at the investigative site or locally; scans will be collected and RECIST 1.1 assessments performed. Collection of disease assessments will continue until progression, start of a new anticancer therapy, death or end of study, whichever occurs first. Thereafter, patients who progressed or started new treatment will be followed for survival via phone contact every 12 weeks \pm 1 week.

AE reporting will begin with administration of first dose of study medication. All AEs occurring within 30 days after the last dose of study treatment will be reported. Serious adverse events (SAE) related and unrelated to trial treatment will be collected for 90 days after the last dose of trial treatment or the start of new anticancer treatment, whichever comes first. Afterwards, only SAEs that are related to trial treatment will be reported. All SAE should be reported to the Sponsor via CTEP Adverse Event Reporting System (CTEP AERS).

Patients who are discontinued from the study due to an unacceptable drug-related AE will be followed for resolution of the AE to Grade 0–1 or stabilization, and monitored for disease status by radiologic imaging until progression or initiation of a new therapy for their cancer, whichever occurs first.

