5.5 Duration of Follow Up

Upon discontinuation of therapy in patients without documented disease progression, every effort should be made to continue monitoring patients' disease status by radiologic imaging either at the investigative site or locally. Imaging will be collected and evaluated per RECIST 1.1.

- Year 1 Post-Treatment: Imaging will be performed Q 3 months (± 14 days) or as clinically indicated for the first year post-completion of treatment.
- Years 2 and 3 Post-Treatment: Imaging will be performed Q 6 months (± 1 month) or as clinically indicated during years 2 and 3 post-treatment.
- If the study remains open, imaging will be performed annually once patient has completed 3 years of follow up for disease assessment.
- Collection of standard of care disease assessments will continue until progression, start of a new anticancer therapy, death or end of study, whichever occurs first.

Patients removed from protocol therapy for unacceptable AE(s) will be followed for resolution or stabilization of the AE or 1 year, whichever is longer, in addition to following for disease assessments.

Disease assessments will be collected until (1) the start of new anticancer treatment, (2) documented disease progression, (3) death, or (4) the end of the study, whichever occurs first.

After progression or start of a new anticancer treatment, patients will be followed for survival ([Section 5.1.1](#)). Time to death will be chronicled for all patients.

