Note: Patients with confirmed progression will be declared as having progressive disease for statistical purposes even if they remain on study and respond continued MK-3575. Responses to continued MK-3575 will be chronicled and reported.

13.5.1.2 **PFS, DOR, and OS**

Survival curves for PFS, DOR, and OS will be estimated using the Kaplan-Meier

method.

For PFS, subjects without documented PD/death will be censored at the last disease assessment date. Any subject who is lost to follow-up will be included in the analysis and their PFS time will be censored on the last date that the subject was known to be progression-free, defined as the date of the last tumor assessment not indicating progression. As a sensitivity analysis, the primary analysis of PFS will be performed reconsidering subjects without documented PD or death who discontinued treatment or received new anticancer therapy to have been progressed at the date of treatment discontinuation or initiation of new anticancer therapy, whichever occurs later.

For OS, subjects without documented death at the time of analysis will be censored at the date last known to be alive.

For DOR, subjects who have not yet progressed by the last disease assessment will be censored at the last disease assessment—this is intended to describe censoring rules for the analysis where only responders are used.

Table 13.1 Analysis Strategy for Key Efficacy Variables

Endpoint/Variable (Description, Time point)	Statistical Method	Analysis Population	Missing Data Approach
Primary Hypothesis			
ORR	Simon Two Stage design analysis	Eligible subjects who receive at least 1 dose of treatment	See 13.5.1.
Secondary Objectives			
PFS	Estimation: Kaplan-Meier method for PFS curve estimation	Eligible subjects who receive at least 1 dose of treatment	Model based (censored at last assessment)
DOR	Summary statistics using Kaplan-Meier method	All responders	Nonresponders are excluded in analysis
OS	Summary statistics using Kaplan-Meier method	Eligible subjects who receive at least 1 dose of treatment	Model based (censored at last date)
Exploratory Objectives			

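### The new-therapy sensitivity analysis for PFS leaves out patients who start new anticancer therapy without progression and later die, so it cannot fully test the 16-month estimate

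*Combined protocol and SAP*

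**What the plan says.** All the relevant rules are in the protocol; the opening of Section 13 says that there will be no separate SAP.

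- **Event.** Section 13.3.1: "Progression-Free Survival (PFS) is defined as the time from randomization to PD or death, whichever occurs earlier, based upon investigator assessment using RECIST 1.1". Section 11.1.5 gives the same two events with a different starting point: "PFS is defined as the duration of time from start of treatment to time of progression or death, whichever occurs first". Neither mentions new anticancer therapy.
- **Censoring.** Section 13.3.1: "Patients without documented PD/death will be censored at the last disease assessment date". Section 13.5.1.2 repeats this. A patient who dies is never censored.
- **Scans.** Section 5.1.1: "Collection of disease assessments will continue until progression, start of a new anticancer therapy, death or end of study, whichever occurs first". Section 5.5 and footnote o of the study calendar agree.
- **Survival.** Section 5.1.1 continues: "Thereafter, patients who progressed or started new treatment will be followed for survival via phone contact every 12 weeks". Deaths after new therapy are therefore captured.
- **New-therapy sensitivity analysis.** Section 13.5.1.2 repeats the PFS analysis "reconsidering subjects without documented PD or death who discontinued treatment or received new anticancer therapy to have been progressed", dated at the later of stopping treatment and starting new therapy.
- **Missed-visit sensitivity analysis.** The note under Table 13.1 censors patients with two or more missed visits before progression at the last assessment before the gap.
- **Use.** Sections 1.2 and 13.2.2 compare PFS at 16 months with a historical 5%. Section 13.5 estimates it by Kaplan-Meier.

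**The concern.** The main rule counts a death whenever it occurs, but the plan stops looking for progression once new therapy starts. For a patient who switches therapy without PD, the interval from the last scan to death is unobserved for progression and is spent on another treatment. The sensitivity analysis is the natural place to show how much this matters. It is restricted to patients with neither PD nor death, so a later death removes the patient from the rule and the late death date stands. Two patients with the same history up to the switch are then handled differently because of vital status after the scans ended.

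What is at stake is how far the sensitivity analysis can be trusted as a lower, more cautious estimate of 16-month PFS.

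**Working it through.** No sample size, power or alpha in the plan depends on this rule, so there is no stated figure of that kind to reproduce. The benchmark is consistent with the cohort in Section 2.1.7: 95% had progressed by 428 days, and 428 / 30.4375 = 14.1 months, which leaves about 5% progression-free shortly before month 16.

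**Step 1. Apply the rules to one history.** Assumed: last scan at month 5, new therapy at month 6, no PD.

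| Later course | Main analysis | Sensitivity analysis as written | Sensitivity analysis, rule extended |
|---|---|---|---|
| Dies at month 20 | Event at 20; event-free at 16 | Event at 20; event-free at 16 | Event at 6 |
| Dies at month 10 | Event at 10 | Event at 10 | Event at 6 |
| Alive at analysis | Censored at 5 | Event at 6 | Event at 6 |

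Only the first row is event-free at month 16 in the sensitivity analysis as written.

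**Step 2. Does the missed-visit analysis cover that row?** Post-treatment imaging is every 3 months in the first year (Section 5.5), so the gap from month 5 to month 20 would span several scan dates. But the note concerns missed visits before progression and names neither death nor new therapy. Scans that the protocol itself ends are not clearly missed. Coverage is arguable at best.

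**Step 3. Effect per patient on the sensitivity estimate.** With n = 50 (Section 13.7) and no other censoring before month 16, the Kaplan-Meier estimate is the proportion event-free. Moving one patient from event-free to an event changes it by 1/50 = 2 points.

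**Step 4. Illustration.** Assumed: 5 of 50 patients have the Step 1 history; the other 45 have PFS times at exponential quantiles with median 9 months. Of those 45, 14 have an event by month 5 and 13 are event-free at month 16.

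- All five die at month 20 (main, and sensitivity as written): (13 + 5)/50 = 36%.
- All five alive, main (censored at month 5): (36/50) × (13/31) = 30.2%. Here 36 = 50 − 14, and 31 = 36 − 5 remain at risk.
- All five alive, sensitivity (event at month 6): 13/50 = 26%.
- All five die at month 10 (either analysis): 13/50 = 26%.

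Sensitivity gap: 36 − 26 = 10 points, or 2 per patient. Main estimate against censoring at the last scan: 36 − 30.2 = 5.8 points, or about 1.2 per patient.

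**Step 5. Vary the assumptions.**

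| Median PFS of others | New-therapy patients | Die at month 20 | Alive, main | Alive, sensitivity |
|---|---|---|---|---|
| 6 months | 5 | 24% | 16.8% | 14% |
| 9 months | 2 | 32% | 29.7% | 28% |
| 9 months | 5 | 36% | 30.2% | 26% |
| 9 months | 8 | 40% | 30.6% | 24% |
| 12 months | 5 | 46% | 41.3% | 36% |

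The sensitivity gap stays at 2 points per patient. With five patients, the main-analysis gap against censoring runs from 4.7/5 = 0.9 to 7.2/5 = 1.4 points per patient. The lowest estimate shown is 14%.

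**The case against.** **The main definition is sound.** PFS to progression or death whatever therapy follows is a recognised treatment-policy choice. A reader might infer that the definition in 13.3.1 is inconsistent and must change. The documents do not support that: it counts every death and censors only patients with neither event. This objection stands, and the point is confined to the sensitivity analysis.

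**The direction depends on when death occurs.** A reader might infer that dying always improves a patient's PFS contribution. At the landmark this needs death after month 16. With death at month 10 the main estimate in the illustration is 26%, below the 30.2% under censoring. This stands.

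**The path is narrow.** The patient must switch without PD, live past month 16 and die before the analysis. Footnote o of the calendar asks for a scan at discontinuation unless one was done within 4 weeks, and Section 11.1.4.3 urges documenting progression even after treatment stops. Both make PD before a switch more likely to be recorded. This stands as to size; the number could be zero.

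**The restriction could mean status when new therapy began.** That reading would include later deaths. But the censoring rule in the same paragraph uses equivalent wording for status at analysis, so it is not the natural reading. If it was intended, the added sentence makes it explicit.

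**Patients who stop treatment, take no new therapy and later die are also left out.** True, but Section 5.5 plans continued scans for those who stop without PD, so their progression-free time is not left unobserved by design. This does not weaken the fix.

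**Conclusion.** The point holds for the new-therapy sensitivity analysis. As written, it misses patients who switch therapy without PD and die after month 16, and the missed-visit analysis does not clearly pick them up.

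The effect is at most about 2 points of 16-month PFS per patient in the sensitivity estimate. That assumes n = 50 and no other censoring before month 16, and it treats a switch as a failure, which is the convention of that analysis rather than an observed progression. A reader might take 2 points as the overstatement in the main estimate. That is not supported, because these patients have no documented PD. Against censoring at the last scan, the illustrated figure is about 1.2 points per patient. The counts and times used are assumptions; the documents give none.

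Nor do the documents support an inference that the comparison with 5% is in doubt: every illustrated estimate is 14% or more. PFS is a secondary endpoint and the ORR test is unaffected. This is a cheap improvement, not a flaw in the design.

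**What to change.** Add one sentence to the sensitivity analysis in Section 13.5.1.2: any patient who starts new anticancer therapy before documented PD is counted as a PFS event on the date that therapy starts, whether or not the patient later dies. Leave the primary PFS definition and its censoring rule unchanged.

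The existing rule already needs the start date of new therapy, and survival follow-up already records deaths, so no new data are required. The downside is a slightly lower sensitivity estimate.
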